5.3 Lifestyle Considerations

5.3.1 Meals and Dietary Restrictions

Participants should maintain a normal diet unless modifications are required to manage an AE such as diarrhea, nausea, or vomiting. Lenvatinib capsules may be administered with or without food.

5.3.2 Contraception

Lenvatinib may have adverse effects on a fetus in utero. Refer to Appendix 5 for approved methods of contraception.

Participants should be informed that taking the study intervention may involve unknown risks to the fetus (unborn baby) if pregnancy were to occur during the study. To participate in the study, WOCBP must adhere to the contraception requirement (Appendix 5) from the day of study intervention initiation throughout the study period up and up to 30 days post

lenvatinib. If there is any question that a WOCBP will not reliably comply with the requirements for contraception, that participant should not be entered into the study.

5.3.3 Pregnancy

If a participant inadvertently becomes pregnant while on lenvatinib, the participant will be immediately discontinued from study treatment. The site will contact the participant at least monthly and document the participant's status until the pregnancy has been completed or terminated. The outcome of the pregnancy will be reported to Sponsor without delay and within 24 hours if the outcome is a serious adverse experience (eg, death, abortion, congenital anomaly, or other disabling or life-threatening complication to the mother or newborn). The study investigator will make every effort to obtain permission to follow the outcome of the pregnancy and report the condition of the fetus or newborn to the Sponsor as described in Section 8.4. If a male participant impregnates his female partner, the study personnel at the site must be informed immediately and the pregnancy must be reported to the Sponsor and followed as described in Section 8.4.

5.3.4 Use in Nursing Women

It is unknown whether lenvatinib is excreted in human milk. Since many drugs are excreted in human milk, and because of the potential for serious adverse reactions in the nursing infant, participants who are breastfeeding are not eligible for enrollment.

5.4 Screen Failures

Screen failures are defined as participants who consent/assent to participate in the clinical study, but are not subsequently entered in the study. A minimal set of screen failure information is required to ensure transparent reporting of screen failure participants to meet the CONSORT publishing requirements and to respond to queries from regulatory authorities. Minimal information includes demography, screen failure details, eligibility criteria, and any AEs or SAEs meeting reporting requirements as outlined in the data entry guidelines.

5.5 Participant Replacement Strategy

A participant who is not evaluable for objective response will be replaced.

6 STUDY INTERVENTION

Study intervention is defined as any investigational intervention(s), marketed product(s), placebo, or medical device(s) intended to be administered to a study participant according to the study protocol.

Clinical supplies will be packaged to support enrollment . Clinical supplies will be affixed with a clinical label in accordance with regulatory requirements.

6.1 Study Intervention(s) Administered

The study intervention to be used in this study is outlined in [Table 2](#).

Table 2 Study Interventions

Arm Name	Arm Type	Intervention Name	Intervention Type	Dose Formulation	Unit Dose Strength(s)	Dosage Level(s)	Route of Administration	Regimen/Treatment Period	Use	IMP or NIMP/AxMP	Sourcing
Arm 1	Experimental	Lenvatinib	Drug	Capsule	1 mg, 4 mg, 10 mg	14 mg/m ²	Oral	Once daily	Test Product	IMP	Central

EEA=European Economic Area; IMP=investigational medicinal product; NIMP/AxMP=noninvestigational/auxiliary medicinal product. The classification of IMP and NIMP/AxMP in this table is based on guidance issued by the European Commission and applies to countries in the EEA. Country differences with respect to the definition/classification of IMP and NIMP/AxMP may exist. In these circumstances, local legislation is followed. After adjustments for body surface area, the lenvatinib daily dose will not exceed 24 mg. A participant who is not evaluable for objective response will be replaced.
											

All supplies indicated in [Table 2](#) will be provided per the "Sourcing" column depending upon local country operational requirements. If local sourcing, every attempt should be made to source these supplies from a single lot/batch number.

Refer to Section 6 for details regarding administration of the study intervention.

6.2 Preparation/Handling/Storage/Accountability

6.2.1 Dose Preparation

Lenvatinib is a capsule for oral administration and does not require preparation. For participants unable to swallow capsules a suspension can be prepared. See the Pharmacy Manual for additional information.

6.2.2 Handling, Storage, and Accountability

The investigator or designee must confirm appropriate temperature conditions have been maintained during transit for all study intervention received, and any discrepancies are reported and resolved before use of the study intervention.

Only participants enrolled in the study may receive study intervention, and only authorized site staff may supply or administer study intervention. All study interventions must be stored in a secure, environmentally controlled, and monitored (manual or automated) area in accordance with the labeled storage conditions with access limited to the investigator and authorized site staff.

The investigator, institution, or the head of the medical institution (where applicable) is responsible for study intervention accountability, reconciliation, and record maintenance (ie, receipt, reconciliation, and final disposition records).

For all study sites, the local country Sponsor personnel or designee will provide appropriate documentation that must be completed for drug accountability and return, or local discard and destruction if appropriate. Where local discard and destruction is appropriate, the investigator is responsible for ensuring that a local discard/destruction procedure is documented.

The study site is responsible for recording the lot number, manufacturer, and expiry date for any locally purchased product (if applicable) as per local guidelines unless otherwise instructed by the Sponsor.

The investigator shall take responsibility for and shall take all steps to maintain appropriate records and ensure appropriate supply, storage, handling, distribution, and usage of study interventions in accordance with the protocol and any applicable laws and regulations.

6.3 Measures to Minimize Bias: Randomization and Blinding

6.3.1 Intervention Assignment

Treatment allocation will occur centrally using an interactive response technology. Participants will be assigned to 1 of 4 cohorts based on their malignancy.

6.3.2 Stratification

No stratification based on age, sex, or other characteristics will be used in this study.

6.3.3 Blinding

This is an open-label study; therefore, the Sponsor, investigator, and participant will know the intervention administered.

6.4 Study Intervention Compliance

Interruption from the protocol-specified lenvatinib treatment ≥ 28 days requires consultation between the investigator and the Sponsor and written documentation of the collaborative decision on participant management.

6.5 Concomitant Therapy

Treatment (including blood products, blood transfusions, fluid transfusions, antibiotics, and antidiarrheal drugs, etc.) for AEs or therapy to ameliorate symptoms may be administered at the discretion of the investigator, unless it is expected to interfere with the evaluation of (or to interact with) the study medication. Prophylactic use of G-CSFs is not permitted.

Administration of systemic corticosteroids for PD is not permitted.

- Administration of systemic corticosteroids will be limited to premedication or the short-term treatment of acute medical conditions in accordance with approved indications, institutional, or national guidelines.
- Inhaled steroids are allowed for management of asthma.

Palliative radiotherapy of up to 2 painful preexisting, nontarget bone metastases will be permitted without being considered PD.

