4.2.1 Rationale for Endpoints

4.2.1.1 Efficacy Endpoints

This study will use ORR, defined as the proportion of participants with confirmed objective response (an objective response of CR or PR at Week 16, based on RECIST 1.1 or RANO for HGG as assessed by the investigator) as the primary endpoint. For single-arm studies, ORR is commonly used to assess clinical activity of therapies in the treatment of pediatric solid tumors. The use of RECIST 1.1 and the use of RANO for HGG to assess ORR is typically considered acceptable by regulatory authorities.

Antitumor activity for participants with neuroblastoma enrolled in the other solid tumors' cohort will be determined by the following criteria and combined with RECIST-based efficacy for assessment of the study endpoints.

- CR: Complete resolution of all MIBG-positive lesions.
- PR: Resolution of at least 1 MIBG-positive lesion, with persistence of other MIBG-positive lesions.
- SD: No changes in MIBG scan in number of positive lesions.

- PD: Development of new MIBG-positive lesions.

DOR, BOR over the treatment period, DCR, CBR, and PFS are secondary endpoints that will serve as additional measures of efficacy and are commonly accepted endpoints by both regulatory authorities and the oncology community.

Overall survival, defined as the time from the first day of study intervention to death due to any cause, will be an exploratory endpoint.

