5.1 Inclusion Criteria

A participant will be eligible for inclusion in the study if the participant:

Type of Participant and Disease Characteristics

1. Has histologically or cytologically documented relapsed, or refractory pediatric solid malignancy excluding osteosarcoma.
Participants with diffuse midline glioma (formerly known as diffuse intrinsic pontine glioma), optic pathway glioma, or pineal tumors with elevated tumor markers (AFP, β -hCG, or hCG) do not require histological or cytological confirmation of diagnosis. Participants with diffuse midline glioma are not eligible for the HGG cohort and should only be enrolled in the other solid tumors' cohort.
2. Has measurable disease as defined by RECIST 1.1 or RANO for HGG, meeting the criteria below:
 - All tumor types except HGG and neuroblastoma: At least 1 lesion measuring ≥ 1.0 cm in the longest diameter for a non-lymph node or ≥ 1.5 cm in the short-axis diameter for a lymph node that is reproducibly measurable on CT or MRI scans.
 - HGG: At least 1 contrast-enhancing lesion with clearly defined margins on T1-weighted MRI scan, measuring ≥ 1.0 cm in 2 perpendicular diameters, and visible on at least 2 axial slices (preferably no more than 5 mm apart with 0 mm gap).
 - Participants with neuroblastoma who do not have measurable disease per RECIST 1.1 but have MIBG-positive evaluable disease may be enrolled.
 - Tumor lesions situated in a previously irradiated area or in an area subjected to other locoregional therapy are considered measurable only if progression has been observed in such lesions since the completion of therapy.

3. Has a performance status as defined below:

- Lansky Play Score ≥ 50 for participants up to and including 16 years of age.
- KPS ≥ 50 for participants >16 years of age.
- Neurologic deficits in participants with primary CNS tumors must have been stable for at least 7 days prior to study enrollment. Participants who are unable to walk because of paralysis, but who can perform ADL while wheelchair bound, will be considered ambulatory for the purpose of assessing the performance score.

4. Demonstrate adequate organ function as defined below:

System	Laboratory Value																				
Hematological																					
For participants without bone marrow involvement																					
ANC	$\geq 1000/\mu\text{L}$																				
Platelets	$\geq 75,000/\mu\text{L}$																				

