6.5.1 Prohibited Concomitant Medications

Participants are prohibited from receiving the following therapies during screening and while on treatment during the study:

- Concurrent anticancer therapies such as chemotherapy, TKIs, radiotherapy (with the exception of palliative radiotherapy as specified in Section 6.5), antitumor interventions (surgical resection, surgical debulking of tumor, etc.), or cancer immunotherapy.
- Concurrent other investigational drugs.

For participants who, in the assessment by the investigator, require the use of any of the aforementioned treatments for clinical management, continuation of the study medication, and further participation in the study must be discussed and agreed upon with the Sponsor.

If participants receive additional anticancer therapies, this will be judged to represent evidence of disease progression, and study medication will be discontinued. These participants should complete all off-treatment assessments and continue to be followed for survival in the Survival Follow-up Period.

Further information on the prohibited concomitant therapies for lenvatinib is included in the prescribing information.

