9.4.1 Efficacy Endpoints

Primary Endpoints

- **ORR:** defined as the proportion of participants with a confirmed (≥ 4 weeks after initial response) CR or PR per RECIST 1.1 or RANO for HGG as assessed by investigator, at Week 16.

Secondary Endpoints

- **ORR.**
- **BOR:** defined as the participant's best confirmed response (CR or PR) over the treatment period.
- **DOR:** defined as the time from the date of the first documented CR or PR to the date of the disease progression objectively documented or death (whichever occurs first).
- **DCR:** defined as the percentage of participants who have a BOR of CR, PR, or SD. To be assigned a best overall response of SD, the time from the first administration of study drug until the date of documented SD should be ≥ 7 weeks.
- **CBR:** defined as the percentage of participants who have a BOR of CR, PR, or durable SD (SD duration ≥ 23 weeks since the first dose of the study treatment).
- **PFS:** defined as the time from the date of the first administration of study drug until the date of first documentation of PD per RECIST 1.1 or RANO for HGG or death (whichever occurs first).

Tertiary/Exploratory Endpoints

- **OS:** defined as the time from the date of the first administration of study drug until the date of death from any cause.

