9.5 Analysis Populations

9.5.1 Efficacy Analysis Population

The EAS population will serve as the primary population for the analysis of antitumor activity data within each tumor type in this study. EAS is defined as all evaluable participants, who have measurable disease present at baseline and at least 1 postbaseline efficacy assessment, unless they have discontinued prior to the first efficacy assessment due to progressive disease. Details on the approach to handling missing data are provided in [Table 5](#).

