9.6 Statistical Methods

9.6.1 Statistical Methods for Efficacy Analyses

This section describes the statistical methods that address the primary and secondary efficacy objectives. Methods related to exploratory objectives will be described in the sSAP.

Antitumor activity data will be analyzed by each tumor type. The data cutoff for the primary study analysis for a given tumor type will be determined by the study team, based on the review of data at each interim analysis and predetermined futility guidance.

Only those participants who have measurable disease present at baseline and have their disease re-evaluated at postbaseline visits will be considered evaluable for ORR. These participants will have their response classified according to RECIST 1.1 or RANO for participants with HGG.

Primary Efficacy Analysis

ORR: Objective responses will count only confirmed CR and PR at Week 16. Estimated ORR and its exact 95% CI using the method of Clopper and Pearson will be presented.

Secondary Efficacy Analyses

The BOR will be provided with the descriptive statistics. The ORR, DCR, and CBR will be provided with exact 95% CIs using the method of Clopper and Pearson, and the DOR will be analyzed for responders using Kaplan-Meier approach.

The secondary endpoint of PFS will be analyzed using Kaplan-Meier product-limit estimates. Median PFS and the cumulative probability of PFS at 4, 6, 12, and 24 months will be presented with 2-sided, 95% CIs when an adequate number of at-risk participants at those time points warrant the estimate. The cumulative PFS probabilities will be plotted over time as appropriate.

A summary of the primary analysis strategy for the key efficacy endpoints is provided in [Table 5](#).

Table 5 Table Analysis Strategy for Key Efficacy Variables

Endpoint/Variable	Statistical Method	Analysis Population	Missing Data Approach
Primary Analyses – Within tumor type			
ORR (RECIST 1.1 or RANO for HGG) at Week 16	Summary statistics using Clopper and Pearson method	EAS	Participants in EAS with missing data are considered nonresponders.
Secondary Analyses – Within tumor type			
ORR	Summary statistics using Clopper and Pearson method	EAS	Participants in EAS with missing data are considered nonresponders.
BOR	Summary statistics using Clopper and Pearson method	EAS	Missing observation in EAS population are counted as nonresponders.

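### Neuroblastoma response: the plan does not exclude lesions irradiated on study, so permitted palliative radiotherapy could be scored as an MIBG partial response

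*Combined protocol and SAP*

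**What the plan says.** Four parts of the combined protocol and SAP bear on this.

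- **Radiotherapy on study.** Section 6.5: "Palliative radiotherapy of up to 2 painful preexisting, nontarget bone metastases will be permitted without being considered PD". Section 6.5.1 carves this out of the prohibited therapies: "radiotherapy (with the exception of palliative radiotherapy as specified in Section 6.5". It is therefore not caught by the rule in that section that treats added anticancer therapy as evidence of progression.
- **Neuroblastoma response.** Section 4.2.1.1, in the rationale for the primary endpoint, gives MIBG criteria. The partial-response line reads: "PR: Resolution of at least 1 MIBG-positive lesion, with persistence of other MIBG-positive lesions". Complete response is resolution of all MIBG-positive lesions. Antitumor activity in these participants "will be determined by the following criteria and combined with RECIST-based efficacy for assessment of the study endpoints".
- **Eligibility.** Section 5.1: "Participants with neuroblastoma who do not have measurable disease per RECIST 1.1 but have MIBG-positive evaluable disease may be enrolled".
- **Endpoint and analysis set.** Section 9.4.1 gives the primary ORR, assessed at Week 16, as "defined as the proportion of participants with a confirmed (≥ 4 weeks after initial response) CR or PR per RECIST 1.1" or RANO for HGG. Section 9.5.1: "EAS is defined as all evaluable participants, who have measurable disease present at baseline and at least 1 postbaseline efficacy assessment". Section 9.6.1: "These participants will have their response classified according to RECIST 1.1 or RANO for participants with HGG". None of these three sections mentions MIBG.

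**The concern.** The only thing in Section 6.5 that shields response assessment from the radiotherapy is the restriction to nontarget lesions. For a RECIST PR that is a reasonable shield, because the target lesions drive the call. The MIBG criteria have no target/nontarget split, no size threshold and no condition on why a lesion disappeared, so the shield does not carry over.

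This is a single-arm study in which a confirmed CR or PR is read as lenvatinib activity, with no control arm to show how often local treatment alone would produce the same call. BOR and the start of DOR rest on the same response call. CBR does too: a PR qualifies without the 23 weeks that stable disease needs. DCR uses the same call but is less sensitive, because a participant who would otherwise be SD for at least 7 weeks already counts.

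**Working it through.** There is no design figure to reproduce: the efficacy interim and sample-size text (Sections 9.7.2 and 9.9) is redacted, and the point does not need it. The check is to follow one participant through the rules and then size one misattributed response.

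**Step 1. Participant with measurable disease.** Suppose a RECIST target lesion in soft tissue, stable, and *k* MIBG-positive bone lesions (*k* ≥ 2), none of them a RECIST target.

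- One painful bone lesion is irradiated. Section 6.5 permits it and it is not PD.
- Assume that lesion turns MIBG-negative and stays negative. This is an assumption; the documents give no rate.
- Lesions resolved: 1. Lesions persisting: *k* − 1 ≥ 1. By Section 4.2.1.1 the MIBG call is PR.
- Confirmation at least 4 weeks later is met for as long as the lesion stays negative, so confirmation is no safeguard.
- The RECIST call is SD. Section 4.2.1.1 says the two are combined but not how, so MIBG PR with RECIST SD may or may not count as an objective response.
- Measurable disease is present, so the participant can be in the EAS.

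**Step 2. Participant with MIBG disease only.** With 1 or 2 MIBG-positive bone lesions, all irradiated and all cleared, the MIBG text gives CR. But Section 9.5.1 requires measurable disease and Section 9.6.1 counts only such participants as evaluable for ORR. Read literally, this participant is in neither numerator nor denominator.

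**Step 3. Search for a rule that blocks Step 1.** The only text on irradiated lesions is in Section 5.1. It decides which previously irradiated lesions count as measurable at entry. Sections 4.2.1.1, 8.2.1, 9.4.1, 9.5.1 and 9.6.1 (with Table 5) have no rule for a lesion irradiated on study.

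**Step 4. Size.** Removing one misattributed response changes ORR by 1/n. The neuroblastoma count is not given. As illustrations, take 9 (the number that triggers a tumor-type interim) and 17 (the cap). Exact Clopper-Pearson 95% limits:

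- 0 of n: upper limit = 1 − 0.025^(1/n).
- 1 of n: lower limit = 1 − 0.975^(1/n); the upper limit solves (1 − p)^n + n·p·(1 − p)^(n−1) = 0.025.

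The interval code reproduces the osteosarcoma result in Section 2.2.1.2: 2 of 30 gives 6.7% (0.8 to 22.1).

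| n | With one misattributed PR | With it removed | Difference |
|---|---|---|---|
| 9 | 1/9 = 11.1% (0.3 to 48.2) | 0/9 = 0% (0 to 33.6) | 11.1 points |
| 17 | 1/17 = 5.9% (0.1 to 28.7) | 0/17 = 0% (0 to 19.5) | 5.9 points |

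**The case against.** The strongest reply is that Section 9 already governs. ORR there is RECIST 1.1 or RANO, Section 8.2.1.4 makes RECIST 1.1 the primary measure for everything except HGG, and the EAS needs measurable disease. On that reading MIBG never enters the primary endpoint. This stands in part. It removes MIBG-only participants from the primary ORR, and it leaves open whether an MIBG PR with RECIST SD counts. It does not settle the matter, because Section 4.2.1.1 says in terms that MIBG results feed the study endpoints, and Section 8.2.1.1 sends MIBG-only participants to that section. The two parts of the plan disagree, and the radiotherapy gap is live under one of the two readings.

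A second reply is that Section 6.5 bars treatment expected to interfere with evaluation. The same section then expressly permits this radiotherapy, and the general clause gives no rule for scoring the lesion. A third is that a lesion which itself determines MIBG response might not be nontarget. That is arguable; the text does not say.

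A reader might infer three stronger things that the documents do not support:

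- *That radiotherapy alone creates a primary-endpoint response as the plan is written.* This depends on Section 4.2.1.1 governing and on a combination rule that is not stated.
- *That one such PR could carry neuroblastoma past the futility rule of no responses in 9.* Section 4.1 provides a tumor-type interim only once 9 evaluable participants of that type are enrolled. Nothing shows this happened, and Sections 1.1 and 4.4 record that enrollment to the other solid tumors' cohort has stopped.
- *That RECIST nontarget CR needs the same correction.* Nothing in this argument shows a fault there.

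**Conclusion.** The gap is real and narrow. If Section 4.2.1.1 governs neuroblastoma response, radiotherapy that the protocol permits can yield a PR, or contribute to a CR, without drug effect. The clearest route is a participant with measurable disease plus a nontarget MIBG-positive bone lesion. MIBG-only participants are affected only if they enter the analysis.

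The effect is on the reporting of neuroblastoma response (ORR, BOR, DOR, DCR, CBR) within the other solid tumors' cohort. No futility or expansion decision is now at stake. Each misattributed response is worth 1/n; how many there are, and n itself, cannot be known from the documents. The conclusion assumes that an irradiated lesion can turn and stay MIBG-negative, and that an MIBG PR can count alongside RECIST SD. Because the data are open-label, these calls should be fixed by rule rather than case by case.

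**What to change.** Before the primary analysis lock:

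1. Add to Sections 4.2.1.1 and 9.6.1: *An MIBG-positive lesion irradiated on study is not counted as resolved for CR or PR; it can still support PD.*
2. Reconcile Section 4.2.1.1 with Sections 9.5.1 and 9.6.1: state how MIBG and RECIST results combine into one response, including MIBG PR with RECIST SD, and whether MIBG-only participants are in the EAS.
3. Confirm that dates and anatomical sites of on-study radiotherapy are recorded. Section 8.1.5.2 covers concomitant medications; the documents do not expressly say that irradiated sites are captured. If they are not, they need to be retrieved for the neuroblastoma participants.

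The radiotherapy permission is unchanged, and no change to RECIST nontarget assessment is proposed.

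The cost is a sentence in two sections, one combination rule, and a derivation for one tumor type. ORR may come out slightly lower, and a true drug response in an irradiated lesion will not be credited. A participant whose unirradiated lesions all clear would be scored PR rather than CR, which leaves ORR unchanged. Treating the irradiated lesion as non-evaluable would also prevent the false PR; whichever is chosen should be written down before the lock.
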